**e. Data Safety Monitoring Plan (DSMC)**

The PI will utilize a standardized approach employing contemporary biostatistical, medical, and ethical principles to review study design and interim data before trial inception and every year thereafter; the PI will also have the ability to ask for more frequent reviews at any time during the study if they deem this necessary. The PI, data manager, and study statistician will prepare a specific report for the IRB. Specific attention will be given to data quality and timeliness, participant recruitment, accrual and retention, participant risk versus benefit, adverse events, and other factors that can affect study outcome, including scientific developments that may have an impact on the safety of the participants or the ethics of the study. The procedures in place for monitoring adverse events as well as for site, data and statistical management will enable us to generate a timely report to the IRB. The data safety report to the IRB will include:

1. All serious and unexpected adverse events (for example, inpatient hospitalizations) or other unanticipated problems that involve risk to study participants or others at either site, and whether these appeared related to the research assessment protocols. Reports will not specifically disclose the session/dose arm of the study unless this is required for safety reasons;

2. Whether participants' safety, privacy, and confidentiality has been consistently assured by the investigator;
3. Whether the PI recommends an interim analysis pertinent to evaluating participants' safety;
4. Judgments as to whether research instruments have been administered in a uniform manner and in a way that maintains participants' confidentiality;
5. A review of the study's progress toward recruitment goals, quality of data (e.g., appropriate completion of forms), medication treatment adherence, and participant retention/attrition rates;
6. A review of new scientific literature pertinent to the safety of participants or the ethics of research participation (for example, new therapeutic developments).  
These reports will be filed with the PI, who will file them with the Human Participants IRBs. The annual reports will also be filed with the IRB. The reports will enumerate the dates that the committee met and its procedures for monitoring participants' safety and confidentiality and data integrity. There will be regular, ongoing communication between the PI and the IRB. IRB protocols and informed consent documents will be annually reviewed by the IRB. The PI will take responsibility for reporting any serious adverse event (SAE) to the IRB within 24 hours according to standard regulations. A SAE is defined as follows: death, life-threatening adverse event, inpatient hospitalization, persistent or significant disability/incapacity, and medically significant event.

- i. Person(s) responsible for Data and Safety Monitoring  
The PI.
- ii. Frequency of DSMB meetings  
NA
- iii. Specific triggers or stopping rules  
See study endpoints.
- iv. DSMB Reporting  
A summary of the report will be submitted to the IRB for review.
- v. Will the Protocol Director be the only monitoring entity? (Y/N)  
Yes
- vi. Will a board, committee, or safety monitor be responsible for study monitoring? (Y/N)  
N

---

**f. Risks to Special Populations**

NA

---

**10. BENEFITS**

Participants may find that the study drug improves cognitive impairment and depressive symptoms, potentially benefiting future participants who struggle with MDD and cognitive impairment.

---

## **11. PRIVACY AND CONFIDENTIALITY**

All participant information and specimens are handled in compliance with the Health Insurance Portability and Accountability Act (HIPAA) and privacy policies of Stanford University, Stanford Health Care, and Stanford Children's Health.

## Statistical Analysis Plan

### **Primary Outcome**

We will evaluate the primary cognitive control circuit measure by testing the effect of 8 weeks of guanfacine immediate release (GIR) using a general linear model (GLM). This model will include a within-subjects factor for treatment (pre- vs. post-treatment sessions) and a within-subjects repeated measures factor for cognitive control circuit function, comprising five measures: task-evoked activation of the dorsal anterior cingulate cortex (dACC), left dorsolateral prefrontal cortex (dLPFC), right dLPFC, and connectivity between these regions. The analysis will assess the main effect of treatment and, secondarily, the interaction between treatment and circuit measure. Planned paired t-tests will evaluate the effect of GIR on changes in individual circuit measures.

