### b. Objectives

The proposed study addresses a public health need, generated by the burden of illness from depression. Major depressive disorder (MDD) is a prevalent and disabling condition; the 1-year prevalence is approximately 17%, and lifetime prevalence is as high as 25% globally. Only a subset of individuals with depression reach symptomatic remission after adequate treatment with first-line antidepressant medication treatment, estimated at approximately 30-40%. Dysfunction in a large-scale neural circuit alternatively called the executive or cognitive control circuit is associated with cognitive symptoms, including executive dysfunction and difficulty concentrating. These are core symptoms of depression and among the most frequently reported untreated symptoms of MDD.

Cognition is central to clinical and quality of life outcomes in depression. Research has repeatedly shown that cognitive impairments are not effectively treated by antidepressant medications. A significant proportion of MDD patients continue to experience debilitating cognitive symptoms even after attaining remission of mood symptoms with antidepressant treatment. These cognitive impairments are implicated in depression relapse and associated morbidity, highlighting the need for novel treatments that improve cognitive dysfunction in depression.

Guanfacine immediate release (Brand Name: Tenex) is an FDA-approved medication for hypertension and is used off-label for ADHD. The extended-release formulation is FDA-approved for treating ADHD in children and adolescents. In this study, we aim to

determine whether guanfacine immediate release (referred to hereafter as guanfacine or GIR) preferentially increases activation in a key node (dorsolateral prefrontal cortex, dLPFC) of the cognitive control circuit in participants with MDD, low baseline activation in this node, and cognitive deficits as compared to placebo as well as guanfacine in MDD participants with high baseline activation. Furthermore, we aim to determine whether change in dLPFC activation is correlated with changes in cognition. If our hypotheses are correct, baseline activation in the dLPFC may serve as a mechanistic neural target for treatment of symptoms with guanfacine in a subgroup of patients with MDD as well as a baseline predictor of response. Thus, this study will move us toward a more personalized and brain-based model of depression.

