**a. Procedures**

1. Recruitment and screening: Participants experiencing depressive symptoms and not taking any psychiatric medications as determined by a 5 half-life wash out period will be recruited from the community, including students and employees at Stanford. Recruitment will come primarily from Facebook ads, which will use only IRB approved material. A flyer will also be physically posted on boards in public locations in order to include a variety of sources for the study.
2. Individuals will need to participate in 3 screening visits in order to enroll in the study. During the first visit, participants will review informed consent, be administered a clinical interview, and be sent instructions for completing cognitive testing at home.
3. If eligibility after this initial screening visit, the second visit will be a medical screen in order to ensure participants are safe to take GIR and will include standard blood tests, medical history, vitals, and a urine drug test.
4. If the participant meets medical and cognitive criteria, functional magnetic resonance imaging (fMRI) scans will be undertaken at another study visit at The Stanford Center for Cognitive and Neurobiological Imaging (CNI). Using a participant's task-evoked activity

in the dorsolateral prefrontal cortex (dLPFC) and performance on objective cognitive testing, we will apply thresholds using established healthy norms to select participants within the cognitive biotype+ group.

5. Participants will receive GIR for a period of 8 weeks sent to their place of residence from Mariner pharmacy.
6. Participants will be seen in-person or virtually by a study clinician at weeks 2, 4, 6, 8, and 10 and an appropriately trained clinical research coordinator at weeks 1, 3, 5, 7, and 9. All subjects will have an fMRI scan after 6-8 weeks of taking GIR. During in-person visits and virtual monitoring, we will assess participants for the following: changes to symptoms, function, and suicidality, adherence to GIR, changes to concomitant medication(s), adverse events (AEs), birth control usage compliance, likelihood of pregnancy (female participants of childbearing potential), and vital signs if appropriate.

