7. If participants wish to continue GIR and their psychiatrist or PCP is willing to prescribe this, they will continue with their current dose for weeks 9 and 10. If they prefer to stop taking GIR and/or they do not have a provider who is willing to continue GIR, the participant will be tapered off the medication.

---

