**e. Alternative Procedures or Courses of Treatment**

There are currently no standard-of-care medications available that specifically target or treat cognitive impairment in depression. Initiation of antidepressant medication, particularly serotonin selective reuptake inhibitors (SSRIs), the first-line treatment for major depressive disorder, may be advantageous to participants. SSRIs typically take a minimum of 6-8 weeks once titrated to therapeutic dose to show therapeutic benefit with regard to symptoms. There are risks associated with SSRI treatment including medication side effects such as nausea, gastrointestinal side effects, increased anxiety, headaches, dizziness, fatigue, and a Black box warning of increasing risk of suicidal ideation in adolescence and young adulthood.

Electing to participate in the current study will delay initiating a trial of SSRI treatment by 6 weeks, but participants will then be able to continue with first-line therapy upon study completion. This information will be disclosed in the consenting process and form as standard-of-care drug.

---

**f. Will it be possible to continue the more (most) appropriate therapy for the participant(s) after the conclusion of the study?**

Upon completion of Week 8 of the treatment period, participants will have the choice of whether they would prefer to continue on the treatment or be tapered off the drug by the study MD during Weeks 9 and 10. To maintain the blind, participants who would like to continue treatment will be cross-titrated or down-titrated on their assigned medication (placebo or guanfacine) while simultaneously up-titrating on guanfacine.

Participants must have a physician willing to prescribe them guanfacine upon termination of the study and provide a note from their physician to the study clinician, or they will be tapered off the drug over the two-week safety phase. Upon request, a letter will be written to notify the physician of the participant's involvement in the study. This would facilitate the option for participants' usual care physician to continue treatment with GIR as part of their ongoing care of the participant after completion of the study.

---

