**g. Study Endpoint(s)**

The endpoint for primary and secondary measures will be 8 weeks after initiation of GIR or placebo, regardless of the study outcomes. Additional measures will be collected at the final endpoint of 10 weeks. If a subject reports a significant adverse event or worsening depression, the participant will be removed from the study. The study will not be terminated prematurely in the event that participants randomized to GIR have greater improvement than participants randomized to placebo.

---

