### b. Commercial Drugs, Biologics, Reagents, or Chemicals

Commercial Product 1	
Name:	Guanfacine hydrochloride immediate release
Dosage:	0.5mg nightly, increase every 3 days until 2mg nightly
Administration Route	Oral
New and different use? (Y/N)	Y

---

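### The protocol describes both a placebo-controlled and a single-arm trial, and the SAP's pre/post-only tests cannot answer the stated aim under either reading

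*SAP*

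**What the plan says.** **Text describing a controlled trial.**
- Protocol 1.b (Objectives) aims to show that GIR preferentially raises dLPFC activation in patients with low baseline activation, "as compared to placebo as well as guanfacine in MDD participants with high baseline activation". It adds a second aim, to correlate dLPFC change with change in cognition.
- Protocol 2.f maintains a blind while tapering patients from "their assigned medication (placebo or guanfacine".
- Protocol 2.g rules out early stopping if "participants randomized to GIR have greater improvement than participants randomized to placebo".
- Protocol 9.e says safety reports will not normally disclose the arm.

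**Text describing a single arm.**
- Protocol 2.a has participants receive GIR for 8 weeks: "All subjects will have an fMRI scan after 6-8 weeks of taking GIR". Of those who wish to go on with GIR and have a willing prescriber, it says "they will continue with their current dose for weeks 9 and 10".
- Protocol 6.b lists one product, "Guanfacine hydrochloride immediate release", and no placebo.
- Protocol 8.a gives one enrolment total, 25. No allocation ratio or randomization method appears.

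**Who is enrolled.** Protocol 2.a: "we will apply thresholds using established healthy norms to select participants within the cognitive biotype+ group". The inclusion criteria (8.h) require Go-NoGo dLPFC activation at or below -0.5 SD of the norm, a score that low on one or more of Maze, Digit Span and Verbal Interference, and HDRS-17 of at least 14.

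**The analysis.** SAP, Primary Outcome: "This model will include a within-subjects factor for treatment (pre- vs. post-treatment sessions". The other factor is the set of five circuit measures. Follow-up and secondary tests are also within-subject, and the SAP describes them as tests of the effect of GIR.

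**The concern.** A reader cannot tell from the documents whether any patient receives placebo, and the analysis does not deliver the stated aim whichever is true. A significant pre-to-post change would be reported as a drug effect, although the model contains nothing that separates the drug from practice, expectancy or the passage of time.

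Selection adds to this. Patients enter because their dLPFC activation was low, and left and right dLPFC are two of the five primary measures. If the selecting scan also supplies the pre value, some rise at the second scan is expected without any drug effect. Maze, Digit Span, Verbal Interference and HDRS-17 are likewise both entry criteria and outcomes.

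**Working it through.** **1. The stated comparisons under each design.**
- *GIR against placebo.* Single-arm: no such patients. Randomized: the data would exist, but the SAP has no arm term, so the comparison is never made.
- *Low against high baseline activation on GIR.* Impossible under either design, because 8.h admits only patients at or below -0.5 SD.
- *dLPFC change against cognitive change.* The data would exist under either design, but the SAP has no test for it.

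This step needs no assumption.

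**2. Size of the regression risk (illustration).** The plan gives no power or reliability figure to reproduce. From the documents: n = 25, entry cutoff -0.5 SD, two-sided 0.05, five measures. Assumed: normal scores; zero drug effect; no dropout; retest correlation r; the mean of screened patients relative to the norm (0, -0.5 or -1 SD); the screening scan is the pre scan; the outcome uses the same Go-NoGo task as entry; entry is on the left/right dLPFC mean; the five measures are three activations and two connectivities on one SD scale, with correlation 0 to 0.5 between them.

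If the screened mean is 0, patients at or below -0.5 SD average -φ(0.5)/Φ(-0.5) = -1.141 SD. The expected rise on the entry measure itself is (1 - r) × 1.141, which is 0.685, 0.456 and 0.228 SD at r = 0.4, 0.6 and 0.8.

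Simulated share of trials with a significant five-measure main effect, with all cross-session correlations scaled by r:

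| Screened mean | r = 0.4 | r = 0.6 | r = 0.8 |
|---|---|---|---|
| 0 | 52-84% | 37-65% | 20-36% |
| -0.5 SD | 27-53% | 20-36% | 12-20% |
| -1 SD | 14-24% | 11-18% | 8-11% |

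**3. Sensitivity to the correlation structure.** Suppose instead that the between-region correlation is 0.5 and stable across sessions. At screened mean 0 the five-measure rate is then about 25% at r = 0.6 and 15% at r = 0.8. The left dLPFC t-test at r = 0.6 is significant in about 30%, against 44-61% under the first structure. At screened mean -1 SD and r = 0.8 the five-measure rate falls to about 6 or 7%.

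**4. Separate baseline scan.** If a scan taken after selection is the pre scan, the simulated rate is 4.7-5.5%.

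**5. Limit of the regression formula.** Take r = 0.6, between-region correlation 0.5 stable across sessions, and screened mean 0. The left/right mean has SD √0.75 = 0.866.
- Correlation of pre left dLPFC with the entry score: 0.75/0.866 = 0.866. Enrolled left mean: -1.141 × 0.866 = -0.988.
- Formula applied to left dLPFC: 0.4 × 0.988 = 0.395 SD.
- Correlation of post left dLPFC with the entry score: ((0.6 + 0.5)/2)/0.866 = 0.635. True regression: 1.141 × (0.866 - 0.635) = 0.26 SD.

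The formula overstates by about half when applied to a region that is not the entry measure.

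**6. Cognitive outcomes.** One low score is enough for entry. At screened mean 0 each entry test therefore averages only -0.24 to -0.56 SD. The six-measure test is significant in 12-44%, 10-29% and 7-17% at r = 0.4, 0.6 and 0.8. At screened mean -1 SD it is 5-8%, 5-7% and 5-6%. No calculation was made for HDRS-17.

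**7. Precision if randomized.** Assume 13 v 12 and no dropout. The 95% CI half-width is t(23) × √(1/13 + 1/12) = 2.069 × 0.400 = 0.83 SD. Adjusted for baseline, t(22) × √(1 - r²) × 0.400 gives 0.76, 0.66 and 0.50 SD at r = 0.4, 0.6 and 0.8.

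**The case against.** The strongest reply is that the operational text is consistent. Procedures, product list, single enrolment total and SAP all describe one arm, and an uncontrolled pre/post study in 25 patients is a legitimate choice. On that view the placebo sentences are unreconciled wording. Much of this stands: single-arm is the better-supported reading, and the design itself is not the error. But the Objectives, the blind and the randomization sentence are current text, and even a single-arm SAP may not label the change an effect of GIR.

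A reader might infer that placebo patients are being pooled into the GIR estimate. The documents do not show this. It would follow only if patients are in fact randomized and the SAP is run as written.

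The objection to the numbers also stands. Retest reliability, the correlation structure and the screened mean are not given. The SAP does not name the task behind its activation measures, and Protocol 3.a names both Go-NoGo and N-back for this circuit. If the outcome task differs from the entry task, regression is smaller. Protocol 8.k mentions three MRI sessions for one task but otherwise describes two, so a baseline scan after selection cannot be excluded.

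**Conclusion.** The concern holds. The protocol contradicts itself on whether there is a placebo arm, and the SAP does not answer the Objectives under either reading. Confidence in this is high, because it rests on the text alone, and it must be fixed before analysis.

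Regression to the mean stands as a conditional risk, with moderate confidence and unknown size. It requires that the screening scan is the pre scan and that entry and outcome share the task. Given that, the five-measure false-positive rate exceeded 5% in every case tried, from about 6% to 84% over r = 0.4 to 0.8, screened mean 0 to -1 SD and two correlation structures. At r = 0.6 and screened mean 0 it was about 25-65%. It would be tempting to read these as bounds, or as evidence that a positive result would be mostly artefact. The documents support neither, since none of the driving inputs is given and a separate baseline scan would return the rate to about 5%. Practice, expectancy and time would remain uncontrolled in a single-arm trial even then.

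**What to change.** State one design in both documents and say which scan is the pre session. If one of the three sessions in Protocol 8.k is a baseline scan after selection, use it.

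**(a) If single-arm.**
- Remove the placebo, blind, randomization and arm wording from Protocol 1.b, 2.f, 2.g and 9.e. Remove the high-activation comparison and the word *preferentially* from 1.b. Keep the rule in 2.g that removes patients for adverse events or worsening depression, because 9.e refers to it for stopping rules.
- Restate the aim as pre-to-post change in low-activation patients.
- Throughout the SAP, replace *effect of GIR* with *pre-to-post change*, and state that the design cannot separate a drug effect from regression to the mean, practice, expectancy or time.
- If the screening scan is the pre scan, report the expected regression, (1 - r) × (screened mean - enrolled mean), as a sensitivity figure. Give it only for the exact measure used for entry, over a stated range of that measure's own r. Do not apply it to left or right dLPFC separately unless that is the entry measure.

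**(b) If randomized.** Correct Protocol 2.a to GIR or placebo, and state the allocation method and ratio. Analyse the GIR-minus-placebo difference at the post-treatment assessment, adjusted for baseline. Drop the high-activation comparison and state the low precision at N = 25.

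**In either case**, add one pre-specified test of dLPFC change against cognitive change, with both variables named and a 95% CI.

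**Cost.** Rewording and one calculation from existing screening scans under (a); a changed model and protocol corrections under (b). Neither needs extra patients or visits. The price is a weaker claim under (a) and a wide interval under (b).

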**h. Eligibility Criteria**

**i. Inclusion Criteria**

- 18-69 years of age (inclusive)

- Go-NoGo fMRI task-evoked dLPFC  $\leq$  - 0.5 SD below the mean of normative sample
- Behavioral cognitive control performance  $\leq$  - 0.5 SD below the mean of normative sample on a Maze, Digit Span, and/or Verbal Interference (Stroop) task administered using WebNeuro
- Score  $\geq$  14 on the 17-item Hamilton Depression Rating Scale-17 (HDRS-17)
- Meets DSM-5 diagnostic criteria for current, past, or recurrent nonpsychotic major depressive disorder established by MINI Plus
- Medication naïve to guanfacine
- Fluent and literate in English, and show non-impaired intellectual abilities to ensure adequate comprehension of the task instructions
- Written, informed consent
- fMRI scanning eligibility, including no evidence of any form of metal embedded in the body (e.g., metal wires, nuts, bolts, screws, plates, sutures), as these produce artifacts when brain imaging. All potential subjects will need to successfully complete the screening forms at the Stanford Center for Cognitive and Neurobiological Imaging (CNI).

ii. Exclusion Criteria

- Presence of suicidal ideations representing imminent risk, defined by a score of  $>$  8 on the MINI-Plus, or by clinician judgement
- Lifetime history of medical illness or injury that may compromise cognitive functioning or interfere with assessments as deemed by the study physician (such as neurological disorders such as seizures or stroke, Parkinson's disease, dementia, or traumatic brain injury)
- Severe impediment to vision, hearing, and/or hand movement likely to interfere with ability to complete the assessments, or are unable and/or unlikely to follow the study protocols
- Pregnant, breastfeeding or unwilling or unable to use adequate birth control throughout the study
- Loss of consciousness for  $>$  10 minutes during lifetime
- Any contraindication to being scanned in the 3.0T scanner at the CNI such as having a pacemaker or implanted device that has not been cleared for scanning at 3.0 Tesla
- Previous or current DSM-5 bipolar disorder (I, II, not otherwise specified) or psychosis
- Meets criteria for DSM-5 alcohol or substance use disorder within the last 12 months
- Meets criteria for current DSM-5 PTSD, OCD, or eating disorder
- Concurrent participation in other intervention or treatment studies

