- Current use of psychotropic medications. If their usual treating physician is supportive, participants who are currently on psychotropics that can be safely tapered may be tapered off to participate but participant must wait 5 half-lives prior to first scan
- Current use of a strong CYP3A4 inhibitor or inducer (macrolide/ketolide antibiotics [clarithromycin, telithromycin], azole antifungals [itraconazole,

ketoconazole, posaconazole, voriconazole], protease inhibitors [atazanavir, darunavir, indinavir, lopinavir, nelfinavir, ombitasvir, paritaprevir, ritonavir, saquinavir], ceritinib, cobicistat, and idealisib), or inducer (apalutamide, carbamazepine, enzalutamide, fosphenytoin, lumacaftor, lumacaftor-ivacaftor, mitotane, phenobarbital, phenytoin, primidone, rifampin)

- Hypotension as defined by SBP  $\leq$  90 and/or DBP  $\leq$  60 on 2 of 3 separate measurements at least 5 minutes apart, bradycardia as defined by HR  $\leq$  55 on 2 of 3 separate measurements at least 5 minutes apart
- General medical condition, disease, or neurological disorder as reported by participant or found on in-person screenings that is deemed by the study physicians to be unsafe for GIR treatment, including kidney or liver impairment that is deemed to be unsafe, EKG abnormalities that are deemed to be unsafe, or cardiovascular disease deemed to be unsafe.
- History of sudden cardiac death in first degree relatives
- Positive drug screen for any substance deemed by the study physician to be unsafe for use with GIR in combination with other information obtained during screening

---

i. **Screening Procedures**

Participants will complete an online eligibility survey, provide informed consent, and attend two screening visits. Screenings include clinical interviews, medical history, cognitive testing, and functional MRI scans to assess dLPFC activation.

---

j. **Participation in Multiple Protocols**

Participants will first be screened via an online REDCap survey in order to determine initial eligibility. Once participants have completed the survey and have been determined eligible, they will continue to an in-person visit where consenting will take place and further screening procedures will be completed.

Participants will be screened for assessment of inclusion and exclusion criteria at the in-person baseline visit. We will ensure that consent is obtained and enrollment completed before personal health information is collected.

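### The primary pre-post analysis has no control term yet reads the change as the effect of GIR; if the low scan that selected patients is also the pre scan, regression to the mean adds to that change

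*SAP*

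**What the plan says.** SAP, Primary Outcome: the aim is to test the effect of 8 weeks of GIR. "This model will include a within-subjects factor for treatment (pre- vs. post-treatment sessions"). The second factor is the circuit measure, with five levels that include left and right dLPFC activation. The main effect of session comes first and its interaction with measure second. Then: "Planned paired t-tests will evaluate the effect of GIR on changes in individual circuit measures". No arm, placebo or comparison group appears anywhere in the SAP. Missing data are handled by listwise deletion.

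Protocol, selection: section 8.h.i requires "Go-NoGo fMRI task-evoked dLPFC" activation at or below -0.5 SD of a normative sample. Section 2.a item 4 applies the rule to the pre-treatment scan visit: "we will apply thresholds using established healthy norms to select participants within the cognitive biotype+ group". Entry also needs an HDRS-17 score of at least "14 on the 17-item Hamilton Depression Rating Scale-17 (HDRS-17") and cognitive performance at or below -0.5 "SD below the mean of normative sample on a Maze, Digit Span, and/or Verbal Interference (Stroop) task administered using WebNeuro".

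Protocol, control: section 1.b sets out to compare low-activation patients on guanfacine with placebo and with guanfacine in high-activation patients. Section 2.f refers to a blind and to assigned placebo. Section 2.g refers to randomization between GIR and placebo. Section 2.a item 6 has only GIR: "All subjects will have an fMRI scan after 6-8 weeks of taking GIR".

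**The concern.** Without a control term, a pre-post difference contains any drug effect together with time, repeat-scanning and placebo effects. The SAP nevertheless attributes the whole change to GIR, and it does not carry either comparison named in the protocol's objective.

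Selection adds a specific bias. When patients are admitted because a noisy measurement was low, a second measurement is on average higher even if nothing has happened. If the admitting scan is the pre value, dLPFC is expected to rise in the hypothesized direction. dLPFC activation is the stated target, so a significant rise could be reported as engagement of that target when it is partly or wholly an artefact of selection.

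**Working it through.** **Step 1. Is the selecting scan the pre scan?** No sentence says so.
- For: section 2.a describes one scan visit before treatment and one after 6-8 weeks; section 8.k pays for one pretreatment session and one at Week 8; section 1.b defines the groups by baseline activation.
- Against: section 8.k also mentions, once, a total of three scanning sessions without describing the third; section 8.g recruits from other imaging studies, so some entrants may have been selected on an earlier scan.

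This makes it likely, but not established.

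**Step 2. Inputs.** From the documents: cut -0.5 normative SD; planned enrollment 25 (section 8.a); two-sided 0.05; listwise deletion. The documents give no power calculation, SD or reliability, so there is no planned figure to reproduce. Assumed: normal scores with SD 1 in normative units, one dLPFC score selects, test-retest correlation r from 0.3 to 0.8, and a mean m of scanned candidates at 0, -0.5 or -1 SD. There is no drug effect.

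**Step 3. Expected rise.** With a = -0.5 - m, the selected pre mean lies φ(a)/Φ(a) below m, and the expected rise is (1 - r) × φ(a)/Φ(a).
- m = 0: 0.352/0.309 = 1.14; rise 0.7 × 1.14 = 0.80 at r = 0.3 and 0.2 × 1.14 = 0.23 at r = 0.8.
- m = -0.5: 0.399/0.500 = 0.80; rise 0.56 to 0.16.
- m = -1: 0.352/0.691 = 0.51; rise 0.36 to 0.10.

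**Step 4. Paired test on the selected dLPFC score.** The variance of change among those selected is (1 - r)² × Var(pre | selected) + (1 - r²). For m = 0, Var(pre | selected) = 1 + 0.5 × 1.141 - 1.141² = 0.27. At r = 0.3 the SD of change is √(0.49 × 0.27 + 0.91) = 1.02, so the standardized rise is 0.80/1.02 = 0.78. Simulated rejection rates, from r = 0.3 to r = 0.8:

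| Mean of scanned candidates | n = 25 | n = 15 |
|---|---|---|
| at the norm | 97-44% | 81-27% |
| 0.5 SD below | 73-24% | 49-16% |
| 1 SD below | 36-12% | 22-9% |

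The n = 15 column illustrates listwise deletion; the documents give no expected loss. Nearly all rejections point towards benefit. If half of the entrants had a separate pre scan, the n = 25 rates fall to 38-14% at the norm and 11-7% at 1 SD below; if all had one, the rate is 5%.

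**Step 5. Which side selects.** The protocol does not say. At the norm, with n = 25 and true scores correlated 0.3, if either side may qualify a patient each side's test rejects 43-15% with correlated session noise and about 27-11% with independent noise. If both sides must qualify, it rejects about 98-50% and 94-34%.

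**Step 6. Five-measure main effect (the formal primary test).** This was tested as the mean of the five changes per patient, n = 25, true-score correlation 0.3. The first range has session noise correlated 0.3, the second independent noise.
- One common SD scale: 63-22% / 32-12% at the norm; 17-8% / 10-6% at 1 SD below.
- Connectivity SD three times larger: 45-16% / 11-7% at the norm; 13-8% / 6-5% at 1 SD below.
- Connectivity SD one-fifth: 72-25% / 49-17% at the norm.

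These are not bounds: with correlations of 0.5 on a common scale, the rate at the norm is 78-28%.

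**Step 7. Secondary outcomes,** if the screening scores serve as baseline. HDRS-17: with the cut of 14 lying 1 SD below, 0.5 SD below or at the screened mean, the paired test rejects 14-7%, 35-12% or 73-24%, towards improvement. Cognition at the norm: 16-6% per selecting test and 27-7% for the six-test main effect; at most 9% if the mean is 0.5 SD below.

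**Step 8. Remedies under no effect.** A between-arm comparison adjusted for baseline (12 v 13) and a paired test with a post-selection pre scan each reject 4.9-5.3%.

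**The case against.** The strongest reply has four parts.

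- *The formal primary test is not a dLPFC test.* This stands. A reader might take 97-44% as the error rate of the primary analysis; the SAP does not support that. Those figures belong to a planned follow-up. For the main effect the bias may be near nil or large, depending on a measurement scale that the SAP does not give.
- *The regression argument rests on an inference.* This also stands. A reader might infer from "Participants will be screened for assessment of inclusion and exclusion criteria at the in-person baseline visit" (section 8.j) that the selecting scan is the baseline scan. Section 8.j makes that the visit at which consent takes place, and section 2.a puts consent at the first visit and the scan at another, so the sentence does not identify the pre scan.
- *The sizes are assumptions.* They are. Only the direction follows from the entry rule, and only if the selecting scan is the pre scan.
- *A small mechanistic study may properly be single-arm.* It may. That justifies the design, but not attributing uncontrolled change to the drug. Nor is the lack of baseline adjustment a separate defect: without an arm term, adjustment could not isolate a drug effect.

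**Conclusion.** The concern holds in two layers. On the text alone, the primary analysis has no control term, attributes change to GIR, and does not match the protocol's stated comparisons; sections 1.b, 2.f and 2.g conflict with section 2.a and the SAP. Conditionally, regression to the mean would inflate dLPFC change if the selecting scan is the pre scan, which is likely but unproven. HDRS-17 carries the same conditional risk, and cognition carries it more weakly.

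It would go too far to say that the trial will produce a false positive, or that the documents show one scan serving both purposes. Still, every reading calls for a change to the SAP. An existing placebo arm is left out of the analysis, or an existing separate pre scan is not named, or neither exists and the causal wording is unsupported. This should be settled before analysis.

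**What to change.** 1. Reconcile sections 1.b, 2.f and 2.g with section 2.a and the SAP. If a placebo arm exists, make the primary test a between-arm comparison of the post score adjusted for baseline, overall and per measure, and treat the secondary outcomes the same way. If a high-activation guanfacine group exists, add that comparison, and note that it does not remove regression to the mean because the groups are selected differently.
2. State which dLPFC score and which scan select patients, what the third scanning session is, and the scale on which the five measures are combined. If a scan exists after selection and before treatment, use it as pre. This removes regression to the mean but not time or placebo effects.
3. If neither exists, report the main effect and paired tests as descriptive pre-post change, not as an effect of GIR.

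The cost is SAP wording and a few lines of code, with no extra scan or patient. The downsides are a less favourable conclusion and lower power if 25 patients are split over two arms. The allocation ratio is not stated. Assuming 12 v 13, 80% power needs a difference of 1.17 residual SD, against 0.58 SD of change for the paired test at n = 25 (the two SDs are on different scales).
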